6.0 Study Design and Procedures

List any collaborating sites where human subjects research will be performed, and describe the role of those sites and collaborating investigators in performing the proposed research (if applicable): This study will be only conducted at University of Illinois. Study space will be rented at Center for Clinical and Translational Science. In addition, UIC nurse will be responsible for performing nasal examination and collecting blood samples. Study personnel – working out of the PI's laboratory - will ensure regulatory compliance, recruit participants, as well as collect and analyze the data. The PI's lab is located on the first floor of UIC College of Pharmacy. Study materials, equipment and all paper copies will be locked in the office of research staff affiliated with the study.

Describe the study design. The description should be capable of meeting the study objectives: This is a two group, two session study. The only eligibility criteria separating the two groups is the smoking status, otherwise the study population will consist of healthy volunteers. Following successful completion of the "Initial Survey", study participants will be scheduled for a 3-hr In-Person Screening visit. At the in-person screening, participants will 1. be consented, 2. provide urine and breath samples, 3. complete surveys, and 4. receive study instructions. After the completion of the "In-Person Screening", study participants will be scheduled for two study sessions, separated by a minimum of 1 week. During the study session, in random order, study participants will receive either intranasal insulin (60 IU) or placebo. This is a cross-over study –participants receiving intranasal insulin will receive placebo next, and vice-versa. Please refer to Table 1 for a summary of the study

session. The sessions will be identical, other than participants receiving intranasal insulin or placebo in random order.

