1.0 Project Summary/Abstract

This program of research focuses on identifying neurologic biomarkers of smoking behavior in order to develop individualized smoking cessation aids. The research team has carefully designed the study protocol to ensure participant safety and confidentiality. This research will include administration of intranasal insulin and a placebo comparator. The intranasal insulin administered is an investigational drug and has been granted IND status by the FDA (IND#129432). During the times of drug effects, we will evaluate a biomarker using non-invasive equipment. Researchers are trained to be vigilant in identifying any side effects associated with the study drug and associated procedures. Anticipated risks of study drugs and equipment have been recognized by the research team and will be discussed as part of the informed consent process. Access to data collection and sensitive patient information will be limited to the Principal Investigator and designated research team. Researchers have quality control metrics in place to assure collection of accurate data, proper documentation of study activities, and predeveloped contingency plans in the event unanticipated problems occur.

Schemas are welcomed and often provide a nice visual reference for the project: The proposed work is a 2-session crossover design study intended to evaluate the effects of intranasal insulin vs placebo in smokers and non-smokers. Study participants will be randomized to either receive Treatment A (intranasal insulin) or Treatment B (placebo) during each session (Figure 1). The washout period will be 1 week in duration. Study participants will consist of healthy smokers and healthy non-smokers. Period 1 represents the first testing session and Period 2 represents the second testing session. As discussed in the above-section, one specific treatment will be administered per session.

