12.0 Statistical Considerations

If a study incorporates qualitative rather than quantitative methods, indicate this and describe qualitative analysis and disregard the rest of this section: This study does not incorporate qualitative data analysis.

Describe how the data will be examined and statistically analyzed to answer the objectives: Go/no-go accuracy will be evaluated in a 2 x 2 repeated measure ANOVA, with group, treatment and treatment x group interaction entered into the model.

Provide a brief sample size calculation or description of sample size calculation. Include methods and assumptions such as loss to follow-up, as appropriate: Effect size is estimated from Luijten et al (2011). In that study, effect size was 0.24.

We anticipate 120 participants completing the study. An a priori power analysis was conducted using G*power 3.1.9.2 for an ANOVA test, repeated measures and within-between interaction. With 2

within and 2 between factors; a base correlation=0.6; power=0.95; alpha=0.05, the total of 120 participants (60 per group) is required to capture an interaction between group and treatment on ERN.

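### The plan does not say that treatment order is balanced within smokers and within non-smokers, and the ANOVA has no period term, so a session-to-session change can shift the group x treatment estimate by chance

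*Combined protocol and SAP*

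**What the plan says.** Section 6.0 sets out the design: "This is a two group, two session study", with crossover of treatments ("participants receiving intranasal insulin will receive placebo next, and vice-versa"). On allocation it says "During the study session, in random order, study participants will receive either intranasal insulin (60 IU) or placebo". The abstract (section 1.0) adds that participants are randomised to one treatment or the other in each session and points to a Figure 1, which is not in the available copy. The available text gives no allocation ratio, method of generating the sequence, blocking or stratification. Section 6.0 also says that the two sessions are the same apart from the spray, so the go/no-go task is performed twice.

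Section 12.0 specifies a "2 x 2 repeated measure ANOVA, with group, treatment and treatment x group interaction entered into the model". No period or sequence term is listed. The sample size is justified as enough "to capture an interaction between group and treatment on ERN", from an effect size of 0.24 and "a base correlation=0.6; power=0.95; alpha=0.05, the total of 120 participants (60 per group) is required".

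**The concern.** The powered effect compares the insulin-minus-placebo difference between smokers and non-smokers, two groups that are not formed by randomisation. In a two-period crossover, each person's difference contains the treatment effect plus or minus any session-1 to session-2 change, with the sign set by order. If the two groups have different order splits, or change by different amounts between sessions, part of that change ends up in the interaction. Balanced order within each group would keep it out by design, and period terms would keep it out by analysis. The available text provides for neither.

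**Working it through.** **Inputs from the plan (section 12.0).** Total 120, 60 per group, correlation 0.6, alpha 0.05, power 0.95, test of the within-between interaction.

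**The plan's own figure.** For 2 groups and 2 measurements, noncentrality = N x 2 x f²/(1 − 0.6), with 1 and N − 2 degrees of freedom. Read as Cohen's f, 0.24 needs N = 48. Read as d (f = 0.12), it needs N = 184, and 120 gives 83% power. N = 120 at 95% power corresponds to f of about 0.148. So 120 does not reproduce from the stated inputs. That is a separate matter. Here I take 60 per group as given and use the effect for which 120 would give 95% power: a contrast of 4 x 0.148 = 0.59 single-session SD.

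**Assumptions not in the documents.** Simple 1:1 randomisation, no carryover, equal variances, and a practice effect π (session 2 minus session 1) of 0.2 to 0.5 single-session SD.

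**Step 1: how practice enters.** A person's insulin-minus-placebo difference is τ − π if insulin comes first and τ + π if it comes second. With insulin-first share p, the group mean is τ + π(1 − 2p). The shift in the interaction (smokers s, non-smokers n) is therefore

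π_s(1 − 2p_s) − π_n(1 − 2p_n).

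If π is common to both groups, its size is 2 x π x |p_s − p_n|.

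**Step 2: how often order is unbalanced.** Two independent Binomial(60, 0.5) counts:
- SD of p_s − p_n = √(2 x 0.25/60) = 0.091
- P(difference of 10 points or more, i.e. 6 participants) = 0.315
- P(15 points or more, i.e. 9 participants) = 0.120
- P(10 or more participants) = 0.082
- P(one given group is 36:24 or worse) = 0.155

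**Step 3: size against noise.** SD of a within-person difference = √(2 x (1 − 0.6)) = 0.894. SE of the interaction = 0.894 x √(2/60) = 0.163 SD. Shifts for a common π:

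| Order difference | π = 0.2 SD | π = 0.5 SD |
|---|---|---|
| 10 points | 0.04 SD (0.25 SE) | 0.10 SD (0.6 SE) |
| 35 v 25 participants | 0.067 SD (0.41 SE) | 0.167 SD (1.02 SE) |

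**Step 4: error rates (8,000 simulated trials per setting, common π).**

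| Order and model | Type I error, π = 0.2 / 0.5 | Power, π = 0.2 / 0.5 |
|---|---|---|
| Simple, no period term, all trials | 4.8% / 4.8% | 94% / 88% |
| Simple, no period term, gap of 10 or more participants | 7% / 15% | 93% / 79% |
| 30:30 in each group, no period term | 4.4% / 2.5% | 94% / 91% |
| Either, with a period term | about 5% | about 95% |

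The π = 0.5 figures can be checked by hand. Practice adds 0.25 to the variance of the differences, so the SE that the model reports is √((0.80 + 0.25) x 2/60) = 0.187. Under simple randomisation this is also the true spread, and power is Φ(0.59/0.187 − 1.98), about 88%. Under exact balance the true spread is 0.163, so the critical value is in effect 1.98 x 0.187/0.163 = 2.27. Type I error is then slightly above 2% and power is Φ(0.59/0.163 − 2.27), about 91%.

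**Step 5: practice that differs by group.** Suppose 36:24 insulin-first in both groups, π_s = 0.5 and π_n = 0.1. The shift is (1 − 1.2) x (0.5 − 0.1) = −0.08 SD, about half an SE, although the order split is the same in both groups. A single common period term leaves this unchanged. With 30:30 in each group, or with period x group in the model, it is zero.

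**The case against.** The strongest reply is that this is chance imbalance, not bias. Over all possible randomisations the expected shift is zero, and type I error stays at about 4.8% even without a period term. That stands. What remains is lost precision and a shifted estimate when the trial that is run happens to be unbalanced.

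A second reply is that the missing period term is the more direct gap. For a common practice effect, adding it restores about 5% type I error and about 95% power whether or not order is stratified, while stratifying alone leaves the test conservative. That also stands, and it is why the model has to change as well as the allocation. A common period term does not deal with practice that differs between groups. That is plausible, since section 6.1 gives smokers nicotine gum and non-smokers ordinary gum before the task, but the documents give no size for it.

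Third, the size depends on assumed practice effects, and at 0.2 SD the loss is small. This is correct.

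A reader might also infer that order is randomised with no regard to smoking status, from a single list. The documents do not support that. The text is silent on strata and lists, and Figure 1 is not shown.

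**Conclusion.** The point holds as a gap in what is specified, with an inexpensive remedy. As written, neither the described allocation nor the model keeps a session-1 to session-2 change out of the powered interaction. With simple 1:1 randomisation of 60 per group, a 10-point order difference is common (32% of trials). It moves the estimate by 0.04 to 0.10 SD for practice effects of 0.2 to 0.5 SD, and average power falls from 95% to about 94% to 88%. These sizes rest on simple randomisation, the plan's correlation of 0.6, no carryover, and practice effects that the documents do not give. The effect is modest unless practice is large. It would be wrong to conclude that the interaction is systematically biased or that its overall type I error is inflated; the calculation shows neither.

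**What to change.** In section 6.0, state that order is randomised 1:1 in permuted blocks of varying size, separately for smokers and non-smokers, with the lists held by the Investigational Drug Service, which already prepares the sprays (section 6.3). If this is already the intended method, the fix here is to write it down.

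In section 12.0, add period and period x group to the model. Both changes are needed. Blocking without a period term leaves the test conservative (type I error about 2.5% and power about 91% at a practice effect of 0.5 SD). Blocks also balance those randomised, not those who complete, and section 12.0 gives no dropout rate, so the period terms cover imbalance from dropout or unfinished blocks.

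The cost is two lists and one or two of the 118 error degrees of freedom. No participants, visits or procedures are added. The lists must be in place before allocation begins, and the model change before the data are unblinded.

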6.1 Procedures and Assessments

Provide a thorough description of all study procedures, assessments and subject activities in a logical and sequential format. Indicate what study activities happen when and where, including, when applicable, a study schedule that notes number and length of study visits for subjects.

Table 3. Outline of Study Session	
TIME	PROCEDURE
8:00-8:30	Determination of session eligibility (urine and breath tests)
8:30-8:50	Nicotine gum break (smokers), generic chewing gum break (non-smokers)
8:50-9:00	Nicotine blood sample
9:00-9:05	POC glucose check
9:05-9:15	Nares exam
9:15-10:00	Relaxation phase (both smokers and non-smokers)
10:00-10:06	Spray administration
10:10-10:30	Equipment setup
10:30-11:40	Go-No/Go task
11:40-11:45	Olfactory function test
11:45-12:00	Discharge procedure (POC measurement)

Study session will begin at 8:00 AM. First, the research coordinator will ensure that the lab has a signed consent form on file from the participant. Smokers will be instructed to smoke the normal amount of cigarettes they usually smoke upon waking prior to each session, then refrain from smoking until the end of the session. For example, if they usually smoke 2 cigarettes upon waking, they will be instructed to smoke 2 cigarettes prior to the first session (30 minutes upon waking) and 2 cigarettes prior to the second session (30 minutes upon waking). Participants will be asked if they have had breakfast. If they did not eat breakfast that morning, research coordinator will give them a granola bar and re-emphasize the importance of eating breakfast. Next, from 8:00 AM to 8:30 AM, urine and breath samples will be obtained by the study coordinator, for verification of absence of alcohol intake. A urine sample will be obtained to rule out illicit drug intake and pregnancy. See Section 6.2 Specimen Considerations for more information on urine sample collection and analysis protocol.

At 8:30, smokers will take a 20-minute nicotine chewing gum (Nicorette gum, 4mg) break, and non-smokers will take a 20-minute generic, non-nicotine chewing gum break. As per the instructions given by Nicorette, smokers will be instructed chew the gum slowly until they experience a tingling sensation, then to place the gum between their cheek and gum until the tingle subsides and repeat until most of the tingle is undetectable. Non-smokers will be instructed to chew the generic gum at their own pace.

At 8:50 AM, research coordinator will administer VANES Questionnaire on REDCap. Following completion of the VANES Questionnaire, a nicotine blood sample will be taken by the study nurse to ensure comparable nicotine levels in participants between the two sessions. In order to synchronize the procedure in both smokers and non-smokers, a blood sample will be taken from non-smokers as well.

Point of care measurement will occur at 9:00, followed by a physical exam of the nares at 9:05. POC glucose will be checked to ensure normal glucose levels. Study nurse will be responsible for conducting nares physical examination. Subjects will relax from 9:15 to 10:00. The blood draw at 8:50 (for the purpose of nicotine level analysis) can cause a rise in cortisol, which remains high for approximately 60 min. The purpose of the relaxation phase is to wait for the stress response to normalize, thereby minimizing its impact at the time of treatment administration and event related potential testing.

Spray administration will occur at 10:00 AM as one spray in each nostril every 3 minutes for the total of 6 sprays (two sprays at 10:00, two sprays at 10:03, two sprays at 10:06). The same spray protocol will be followed for administration of both intranasal insulin and placebo. AeroPump delivers 0.1 ml of liquid per spray. Since the concentration of insulin in Novolin R is 100 IU/mL, six sprays will deliver the 60 IU intranasal insulin dose. See Section 6.3 Drug Product Considerations for more information on insulin and placebo intranasal administration preparation.

Computerized task testing will occur at 10:30. During the Go/No-Go task, study participants will be instructed to respond as “quickly and accurately as possible” with their right index finger every time the target (“Go”) stimulus (a white “X”) appears, and to withhold a response when the distracter “No/Go” stimuli (a white “K”) appears. Targets will appear with higher frequency (84%, 412 trials with 206 for each run) than distractors (16%, 78 trials with 39 for each run) to establish a strong stimulus-response mapping on “Go” trials. In the second task, visual stimuli will be presented every 1000 ms, each for 100 ms duration, for a total of 400 trials (divided into two 200 trial blocks, separated by a 30-s break). The target stimulus will be a 3.5-cm diameter blue circle (presented 15% of trials), the standard stimulus will be a 3.0-cm diameter blue circle (presented 70% of trials), and the distracter stimulus will be an 18-cm² black and white checkerboard (presented 15% of trials). Participants will be instructed to respond via button press as quickly as possible to target stimuli using the index finger of their dominant hand.

At 11:40 AM, the olfactory function test will be administered by a study coordinator. Olfactory function test will use the Sniffin’ Sticks protocol as outlined in Section 7.0 Expected Risks/Benefits.

[figure not shown]
Discharge procedure will occur at 11:45 AM. Study participants will be given instructions for the next session (or will be provided assent document in the event this is the second session). Their POC glucose will be checked to ensure normal glucose levels. Section 11.0 “Data and Safety Monitoring” provides further details regarding implementation of safety measures in the study, and how potential cases of hypoglycemia will be handled.

Indicate which procedures are standard of care and which procedures are being done for research purposes: None of the procedures in this research study are standard of care. They are all being done for research purposes.

6.2 Specimen Considerations

Describe the specimens to be collected: Urine drug specimens and blood samples will be collected from participants prior to screening and testing procedures. Urine specimens will be used to perform urine drug screens and pregnancy tests. Blood samples will be used to determine nicotine blood levels. Blood samples will also be used to monitor blood glucose levels during the study.

Describe aliquoting and any plans for retention specimens: Samples will be collected at the UIC Center for Clinical and Translational Science. Blood specimens used for nicotine test will be transported to UIC Research Resources Center for analysis. Urine specimens and blood samples collected for POC glucose check will not undergo aliquoting or be retained for future use.

Describe tracking and labeling system: The label (Figure 4) includes the information that will be on the urine collection cup during urine drug screen and urine pregnancy testing or on the blood sample collection vial during nicotine blood test. Researchers will document test results from urine screening on the study flowsheet.

Describe where the specimens be stored and who will be responsible for care of specimens during storage: Urine specimens and blood samples will not be stored for future use.

Describe how long the specimens will be kept: Urine specimens will be disposed immediately after drug and pregnancy screen. Blood samples used for POC blood glucose testing will be disposed immediately after blood glucose check. Following study completion, blood specimens for nicotine testing will be frozen at the UIC Center for Clinical and Translational Science for up to 6 months before transport on dry ice to UIC Research Resources Center. Urine drugs screens, pregnancy tests, and POC glucose checks are expected to take approximately 5 minutes each.

Describe how specimens will be destroyed at study completion: Urine and blood specimens will not need to be retained by researchers until study completion. Urine specimen will only need to be collected for drug and pregnancy screen during the in-person screening and prior to both testing session. Following drug and pregnancy screen, all urine specimens will be disposed immediately as noted above. Following POC blood glucose check, all blood specimens will also be disposed immediately. Following study completion, blood specimens for nicotine testing will be stored and shipped to UIC Research Resources Center as noted above.

Describe how specimens will be analyzed (type and state of development of assay, controls): The research team will conduct and analyze urine drug screens at the beginning of each testing session. The research team is equipped with supplies and has undergone training to perform urine drug

screens and pregnancy screens. For the drug screening, participants will first be asked to provide a urine specimen. A member of the research team will verify the temperature strip on the collection cup is between 90 – 100°F. Researchers will immerse a 12-panel drug screen dipcard into the urine specimen for 10 seconds and analyze the results in 5 minutes. For pregnancy testing, researchers will immerse an HCG test strip into the urine specimen for 3 seconds and analyze results in 5 minutes. Testing supplies used for drug and pregnancy screens are FDA approved with approximately 99% accuracy of test results.

The research team will perform pregnancy testing using AccuMed HCG test strips by immersing the HCG test strip into the urine specimen for approximately 3 seconds and reading the results after 5 minutes. AccuMed HCG test strips are easy-to-use and provide quick and accurate test results. The test strips provide early pregnancy detection with HCG sensitivity levels as low as 25 mIU/mL. This product is FDA approved and provides over 99% accuracy of results.

Each POC blood glucose check will be conducted by a study nurse using the Accu-Check Performa glucometer. A glucose test strip will be inserted into the glucometer. The study nurse will then prick the participant's finger with the lancing device and place the end of finger with the blood drop to the test strip. Blood glucose will be read by the meter and displayed within 5 seconds.

6.3 Drug Product Considerations

Name and description of product: The drug substance used for preparation of the final drug product will be bulk Novolin R. Novolin R is a sterile, clear, aqueous, and colorless solution that contains human insulin (rDNA origin) 100 units/mL, glycerol 16 mg/mL, metacresol 3 mg/mL, zinc chloride approximately 7 mcg/mL and water for injection. The pH is adjusted to 7.4. Hydrochloric acid 2N or sodium hydroxide 2N may be added to adjust pH. Novolin R vials are latex-free. The drug substance is being purchased from McKesson. The placebo utilized in this study is 14% sodium chloride in sterile water.

Route of administration, dosing, dosage regimen and duration: Intranasal insulin will be prepared by University of Illinois Hospital and Health Sciences System Investigational Drug Service. The service is located in the Hospital Pharmacy and contains a segregated compounding area with a biological safety cabinet (BSC). The drug product will be compounded in the BSC using aseptic technique. The pharmacist or a pharmacy technician designee will prepare the requisite drug product following personnel hand hygiene and garbing procedures according to USP<797>. Aero Pump nasal spray system is manufactured in ISO Class 7 environment, hence sterilization of the system prior to compounding procedure will not be necessary. Aero Pump and Novolin R vial will be placed into the BSC. A volume of 3.3 mL Novolin R will be withdrawn using a set of sterile needle and syringe followed by emptying the contents of the syringe into the AeroPump glass bottle. The bottle will then be capped with AeroPump nasal spray. Finally, sterile gauze will be sprayed with sterile IPA following which 20 sprays will be pumped into the gauze for the purpose of priming the final drug product.

Placebo will be prepared using the aseptic technique as described for intranasal insulin. The pharmacist or a pharmacy technician designee will transfer 2.7 mL of sterile water and 4 mL of sterile 23.4% NaCl solution into a sterile container with 10 mL capacity. A volume of 3.3 mL of 14% NaCl

solution will be aseptically placed in the Aeropump spray as describeda. The final step will be the same priming procedure as for insulin spray.

The directions for spray administration will be one spray in each nostril every 3 minutes for the total of 6 sprays delivered over 6 minutes. AeroPump delivers 0.1 ml of liquid per spray. Since the concentration of insulin in Novolin R is 100 IU/mL, six sprays will deliver the 60 IU dose. Aero Pump and Novolin R vial will be placed into the BSC. A volume of 3.3 mL Novolin R will be withdrawn using a set of sterile needle and syringe followed by emptying the contents of the syringe into the AeroPump glass bottle. The bottle will then be capped with AeroPump nasal spray. Finally, sterile gauze will be sprayed with sterile IPA following which 20 sprays will be pumped into the gauze for the purpose of priming the final drug product.

Placebo will be prepared using the aseptic technique as described in the above paragraph. The pharmacist or a pharmacy technician designee will transfer 2.7 mL of sterile water and 4 mL of sterile 23.4% NaCl solution into a sterile container with 10 mL capacity. A volume of 3.3 mL of 14% NaCl solution will be aseptically placed in the Aeropump spray as described in the “Drug Product” paragraph. The final step will be the same priming procedure as for insulin spray.

Describe how any adverse events or serious adverse events will be handled: Section 11.0 describes in detail study procedures which will be implemented to 1. Ensure thorough and accurate collection of AEs and UPs, 2. Timely reporting to the Institutional Review Board, and 3. Follow-up and resolution of all potential AEs and UPs.

List/describe the expected adverse events based on the product label: Expected adverse events from an investigational study conducted with intranasally administered Novolin R (IND#120700) are listed below:

- Local (nasal): anosmia, nasal irritation, local tissue damage
- Cognitive: confusion, visual disturbances
- Others: sweating, shaking, hunger, tingling sensation around the mouth

Expected adverse events from the product label for Nicorette gum are listed below (Nicorette Informational Pamphlet, 2017):

- Central nervous system: Depression, dizziness, headache, insomnia, lack of concentration, nervousness, pain, paresthesia
- Dermatologic: Diaphoresis
- Gastrointestinal: Aphthous stomatitis, constipation, diarrhea, dysgeusia, dyspepsia, flatulence, gingival hemorrhage, glossitis, hiccups, nausea, sialorrhea, stomatitis, tooth enamel damage (abrasions), xerostomia
- Dermatologic: Skin rash
- Hypersensitivity: Hypersensitivity reaction
- *Local: Application site reaction, localized edema, localized erythema*
- *Neuromuscular & skeletal: Arthralgia, jaw pain, myalgia*
- Respiratory: Cough, sinusitis

